**9.8.9 Local laboratory assessments – only during major surgeries**

Blood samples for FVIII activity and haematology must be collected according to flowchart [2.1](#) for central lab analysis. The Investigator/Surgeon should perform local lab assessments at his/her discretion to ensure optimal treatment with N8-GP during major surgery. Only central lab data will be reported.

**9.8.9.1 FVIII activity**

The Investigator/Surgeon should perform local laboratory assessments of FVIII activity during surgery and the post-operative days in order to be able to adjust the dose level of N8-GP to aim for the recommended FVIII plasma activity level, see Section [7.1.4.2](#).

Local assessments of FVIII activity can be performed with either chromogenic or one-stage clotting assays. Glycopegylation has been reported to influence the FVIII activity in aPTT based one-stage clotting assays. Therefore careful validation and qualification of specific assays and conditions are necessary for the assessment of FVIII activity in samples containing N8-GP. Interference is avoided when using an N8-GP reference standard as calibrator in the assay. A reference standard provided by Novo Nordisk must be used when running the assays. The reference standard will be provided by Novo Nordisk together with a description of how to handle, store and use it.

Dependent on the type of aPTT reagent used by the local laboratory an exemption from this requirement can be made. In such cases Novo Nordisk will need to approve the suggested assay on an individual basis. For approval of aPTT based assays the investigator must contact Novo Nordisk.

**9.9 Pharmacokinetics**

Only applicable in case of antibody development, see section [9.8.8.1](#)

**9.10 Pharmacodynamics**

Not applicable for this trial

**9.11 Genetics**

Not applicable for this trial

**9.12 Biomarkers**

Collection of samples for biomarker research is part of this trial as part of the retention for biosamples in [Appendix 7](#). The following samples are required and will be collected from all patients in this trial as specified in the flowchart, see section [2](#):

Patients < 12 years will only have blood samples taken, if maximum limit for blood sampling is not exceeded.

**9.13 PRO questionnaires**

The PRO questionnaires should be completed EoT according to the flowchart in section [2](#). The PRO questionnaire used throughout the trial should be based on the patient’s age at screening. The PRO questionnaire measures treatment satisfaction (Hemo-Sat).

**Table 9-8: PRO questionnaire to be completed by the patient and/or parent(s)/LAR**

Age at screening	Questionnaire to be filled in
16 years or younger	Hemo-SAT Parents
17 years or older	Hemo-SAT adults

## 10 Statistical considerations

Novo Nordisk will be responsible for the statistical analyses.

### 10.1 Sample size determination

All patients participating in NN7088-3859 (pathfinder2) or NN7088-3885 (pathfinder5) fulfilling the inclusion and exclusion criteria of this trial will be eligible to participate where continuous safety assessments will be made. Given that at least 150 patients participate in this trial, the background incidence rate could be up to 0.02 for a given adverse event that was not observed, i.e. the 95% upper bound on the rate of occurrence is 0.02.

### 10.2 Definition of analysis sets

In general, safety endpoints will be reported for Safety Analysis Set while efficacy endpoints will be reported for Full Analysis Set (FAS). These analysis sets are described below.

The patients or observations to be excluded, and the reasons for their exclusion must be documented before database lock. The patients and observations excluded from analysis sets, and the reason for this, will be described in the clinical trial report.

#### **Safety analysis set**

All patients enrolled in the trial have previously been exposed to trial product and therefore all enrolled patients will be included in the Safety Analysis Set. The trial patients will be analysed according to the received treatment.

#### **Full analysis set**

All patients exposed to at least one dose of trial product in the current trial will be included in the Full Analysis Set. The trial patients will be analysed according to the received treatment.

Exceptional outlier plasma activities may be excluded when analysing pharmacokinetic-related endpoints based on the FAS. Default rules for exclusion are described in the paragraph on pre-dose FVIII activity level. Decision to exclude additional FVIII activity measurements from analysis based on the FAS may be made during a review prior to database lock according to ICH-E9, and it will be the joint responsibility of the clinical pharmacology scientist and the trial statistician to decide upon this. The observations to be excluded from the FAS and the reason for their exclusion will be documented and signed by the clinical pharmacology scientist and the trial statistician as part of the database lock minutes. This will also be described in the clinical trial report. The documentation will be stored together with the remaining trial documentation.

Protocol  
 NN7088-4410

~~CONFIDENTIAL~~

Date:	18 June 2019	Novo Nordisk
Version:	2.0	
Status:	Final	
Page:	54 of 86	

### 10.3 Statistical analyses

If necessary, a statistical analysis plan (SAP) may be written in addition to the protocol, including a more technical and detailed elaboration of the statistical analyses. The SAP will be finalised before database lock.

#### 10.3.1 Primary endpoint

##### Number of adverse events reported

All reported AEs will be considered treatment emergent adverse events since all patients had been treated with N8-GP in other pathfinder trials prior to participation in this trial. All AEs, serious adverse events (SAEs) and adverse events of special interest (AESIs) will be summarised by frequency of events and frequency of patients with any event. Furthermore, all AEs will be summarised by severity and causal relation to trial product. In addition, listings will be provided displaying all AEs, SAEs and AESIs.

#### 10.3.2 Secondary endpoints

For all endpoints based on bleeding episode data, only bleeding episodes treated with N8-GP will be included.

Multiple bleeding locations occurring from the same event (e.g. due to a bicycle accident) or at the same time point will be counted as one bleeding episode.

A re-bleed is defined as a worsening of symptoms in the same location after an initial period of improvement, either on treatment or within 72 hours after completed treatment. If a bleeding episode occurs in the same location later than 72 hours after completed treatment it is considered a new bleeding episode.

##### 10.3.2.1 Supportive secondary endpoints

###### Incidence of FVIII inhibitors $\geq 0.6$ BU

The number of inhibitor patients will be reported and all inhibitor data will be presented.

###### Number of bleeding episodes on prophylaxis

The ABR of treatment requiring bleeding episodes will be estimated by a Poisson regression model with logarithmic prophylaxis duration as offset and allowing for over-dispersion. Over-dispersion will be estimated as Pearson's chi-square statistic divided by the degrees of freedom. The estimated ABR will be presented together with a two-sided 95% confidence interval. For sub-groups with no bleeds or less than 5 patients, the 95% confidence interval will not be presented. A sensitivity analysis based on a negative binomial regression model with number of bleeding episodes requiring treatment as the outcome variable and adjusting for exposure time will also be performed.

The analysis of ABR will be repeated as a sensitivity analysis to investigate the potential impact of early withdrawals by imputing number of bleeding episodes for withdrawals. For patients withdrawing prematurely, the number of bleeding episodes counting in the analysis will be imputed up to what they could be expected to have had if they had completed the trial. If e.g. a patient withdraws after 12 months with 5 bleeding episodes, but the patient should have been in the trial for 24 months, then this patient will in the sensitivity analysis count as having had 10 bleeding episodes in 24 months. This is similar to LOCF and will prevent a downwards bias in ABR caused patients with many bleeding episodes withdrawing early. If a patient changes from once weekly to one of the more frequent dosing frequencies, then when doing the sensitivity calculation for once weekly, bleeds during time on the more frequent dosing is calculated using LOCF based on the previous period on every seven day dosing. This is also the case if a patient changes from every seven day dosing more than once, i.e. for each period on more frequent dosing the bleeds for every seven day dosing is imputed based on the previous consecutive period on every seven day dosing.

ABR for each treatment regimen (once weekly, twice weekly, and three times weekly) will be estimated by age group (0-5 years, 6-11 years, 12-17 years and 18- years).

ABR will also be estimated by doing the following further sub-groupings:

- Cause of bleed (spontaneous and traumatic)
- Location of bleed. No sensitivity analyses will be done for this sub-grouping (neither using negative binomial modelling nor using imputation).
- Country. No sensitivity analyses will be done for this sub-grouping (neither using negative binomial modelling nor using imputation).
- Race. No sensitivity analyses will be done for this sub-grouping (neither using negative binomial modelling nor using imputation).
- Ethnicity. No sensitivity analyses will be done for this sub-grouping (neither using negative binomial modelling nor using imputation).
- Month in trial. No sensitivity analyses will be done for this sub-grouping (neither using negative binomial modelling nor using imputation).
- Time since last dose (0-24 hours, 24-48 hours, 48-72 hours and >72 hours). No sensitivity analyses will be done for this sub-grouping (neither using negative binomial modelling nor using imputation).

#### **Number of spontaneous bleeding episodes on prophylaxis**

Included in the above description of ABR by cause of bleed.

#### **Haemostatic effect of N8-GP when used for treatment of bleeding episodes assessed as: Excellent, Good, Moderate, or None**

Haemostatic effect will for each treatment regimen (once weekly, twice weekly, and three times weekly) be summarised by age group (0-5 years, 6-11 years, 12-17 years and  $\geq 18$  years).

Haemostatic effect will be summarised according to:

- Response expressed as excellent, good, moderate, none.
- Success or failure, where success will be defined as a response of good or excellent and failure will be defined as moderate, none or missing
- Success or failure after exclusion of bleeds with missing evaluation of haemostatic response, i.e. success will be defined as a response of good or excellent and failure will be defined as moderate or none information.

Furthermore, success rates will be estimated with 95% confidence intervals using logistic regression accounting for repeated measures within patient assuming compound symmetry working correlation. Age group will be included as a factor and modelling done separately for each treatment regimen. This estimation will be done both including missing haemostatic evaluations as failures and excluding missing evaluations.

Summaries will also be done for the following further sub-groupings:

- Cause of bleed (spontaneous and traumatic). Estimation of success rates and 95% confidence intervals using above described modelling will also be performed (both including missing as failures and excluding missing).
- Location of bleed.
- Severity.
- Country.
- Race
- Ethnicity

#### **Number of N8-GP injections required per bleeding episode**

This endpoint will be summarised and listed.

#### **Pre-dose FVIII activity levels on N8-GP prophylaxis**

The following rules will be implemented for FVIII pre-dose and post-dose activity to ensure data representing steady-state on a given treatment regimen:

- FVIII activity data prior to the 4th prophylaxis dose will be excluded for each switch in treatment regimen
- FVIII activity data will be excluded if post-dose activity is  $\leq$  pre-dose FVIII activity
- FVIII activity data will be excluded if post-dose sample is taken more than 90 minutes after dosing
- FVIII activity results will be excluded for plasma samples defrosted during transit.

Protocol  
NN7088-4410

~~CONFIDENTIAL~~

Date:  
Version:  
Status:  
Page:

18 June 2019  
2.0  
Final  
57 of 86

Novo Nordisk

The pre-dose FVIII activity levels will be modelled to get an estimate of the pre-dose level for N8-GP at steady-state. The model will be a mixed model on the logarithmic plasma activity levels with age as a factor and patient as a random effect. Separate modelling will be performed for each treatment regimen. Plasma concentrations below lower limit of quantification (LLOQ) will be set to half the value of the LLOQ. The estimated pre-dose FVIII level will be presented together with the 95% confidence intervals.

A sensitivity analysis will be performed including all activity results except activities measured in relation to the first 4 prophylaxis doses after switch of treatment regimen.

Pre-dose activity will furthermore be summarised by visit and treatment regimen.

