a.	Transferred from previous trial by sponsor. Note that FVIII recovery cannot be transferred and must be sampled. Date of birth will not be transferred.
b.	Demography consists of date of birth and age (unless not allowed according to local regulation, see Appendix 8 ), ethnicity and race (unless not allowed according to local regulation, see Appendix 8 ).
c.	Training must take place at visit 1 and whenever needed afterwards.
d.	Sampling for FVIII activity and antibodies should be scheduled to allow for a wash out of approximately 3 days. Post-dose FVIII activity must be collected 30± 10 min at visits including administration of trial product.
e.	Post-dose FVIII activity and Lupus anticoagulant should be collected if reduced effect of N8-GP or FVIII inhibitor development is suspected.
f.	Lupus anticoagulant sample only.
g.	Will be transferred from previous trial. Patients who have turned 17 years during their participation in NN7088-3859 (pathfinder2) or NN7088-3885 (pathfinder5) will have to fill in the questionnaire.
h.	For patients > 18 years of age, height will only be assessed at visit 1, 5 and EoT.
i.	For selected countries, and if permitted by local regulations, the investigator may offer to send trial product and auxiliaries to the patient's home by courier service. The bodyweight and height may be re-used from the previous visit. For these patients visit 2, 4, 6 and 8 may be conducted as a phone visit.
j.	Only applicable for patients, who have signed the informed consent for Human biological specimen for long term storage. Patients < 12 years will only have blood samples taken, if maximum limit for blood sampling is not exceeded (  ).
k.	In case of severe allergic reactions see section 9.8.8.3

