**Figure 9-1 Visit structure**

Next visit in line must be calculated based on screening/V1.

Review of completed diaries, PRO questionnaires for possible AEs, and laboratory reports must be documented either on the trial documents or in the patient's source documents. If clarification of entries or discrepancies in the diary or possible AEs in PRO questionnaires is needed, the patient must be questioned and a conclusion made in the patient's source documents. Care must be taken not to bias the patient.

Informed consent must be obtained before any trial related activity, see [Appendix 3](#).

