**9.8 Safety assessments**

Assessments at visits must be performed prior to any trial product administration unless otherwise specified.

Planned time points for all safety assessments are provided in the flowchart.

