#### 9.8.7.1 FVIII activity

Blood samples for FVIII activity will be collected pre-dosing (trough level) and 30 min post-dosing (recovery level) according to flowchart section [2](#). Note that samples taken post dose must not be taken from the same vein as used for administration of N8-GP.

Plasma FVIII activity will be measured with a chromogenic assay. The analysis will be performed at a laboratory selected by Novo Nordisk.

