### 9.8.8 Immunogenicity assessments

#### 9.8.8.1 Evaluation of FVIII inhibitors and antibodies

Blood samples will be analysed for antibodies according to the flowchart see section [2](#):

- FVIII inhibitors

 The trough level is defined as the lowest level of FVIII measure immediately prior to doing and reported as IU/mL

 Recovery level is the FVIII level 30 min after trial product administration relative to the dose administered and will be reported as (IU/mL)/(U/kg)

Protocol  
NN7088-4410

~~CONFIDENTIAL~~

Date:  
Version:  
Status:  
Page:

18 June 2019  
2.0  
Final  
49 of 86

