**Novo Nordisk**

- Anti N8-GP antibodies
- Anti PEG antibodies

All per protocol inhibitor samples are to be analysed by the central laboratory, and only these results will be used in the trial data analysis.

If FVIII inhibitor development is suspected e.g. an increased number of spontaneous bleeding episodes, bleeding episodes difficult to treat, or FVIII recovery and FVIII trough levels below expected values are observed, additional inhibitor tests can be taken at Unscheduled Visits. A wash-out of approximately 3 days is required prior to blood sampling. All FVIII inhibitor tests must be analysed by the Central Laboratory. Please refer to [Appendix 2](#) for the required blood samples for suspicion of inhibitors.

If the Investigator decides to send a sample for inhibitor testing to a local laboratory, the Investigator must also send a duplicate sample for inhibitor testing to the central laboratory. The data from the Central Laboratory will then be used in the official analysis. Any single positive inhibitor test must be reported as an AESI, see [Appendix 4](#).

A positive FVIII inhibitor test is defined as  $\geq 0.6$  BU. A patient is considered to have developed an inhibitor if two separate samples have been tested positive ( $\geq 0.6$  BU) for inhibitors at the central laboratory preferably with no more than 2 weeks between the tests.

In the event that a patient has a single positive test for FVIII inhibitors ( $\geq 0.6$  BU), the patient must attend an unscheduled visit as soon as possible or within 1 week after the result is available to take a confirmatory inhibitor test on a separately drawn sample. Please refer to [Appendix 2](#) for the required blood samples for confirming inhibitors.

These samples should preferably be taken prior to any change of treatment and after approximately 3 days wash-out period. A longer wash out period can be applied if the approximately 3 days wash out is not sufficient to avoid drug interference in the FVIII inhibitor assay.

If the second (confirmatory) inhibitor test is negative the patient will be regarded as inhibitor negative and continue in the trial as per protocol.

If the second (confirmatory) inhibitor test is positive, the patient will be regarded as confirmed inhibitor positive and he must be discontinued if:

- FVIII inhibitor  $> 5$  BU or
- FVIII inhibitor  $\geq 0.6$  and  $\leq 5$  BU and treatment (prophylaxis or treatment of bleeding episodes) with N8-GP is clinically ineffective

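### Pre-dose FVIII is estimated per regimen with no record of time since last dose, so the output cannot show what the estimate represents; the 90-minute exclusion also needs narrower wording (minor)

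*Protocol*

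**What the plan says.** Protocol 10.3.2.1 (pre-dose FVIII activity), repeated in SAP 2.3.2.1, fits one model per regimen: "The model will be a mixed model on the logarithmic plasma activity levels with age as a factor and patient as a random effect". The result is described as the steady-state pre-dose level. The only other planned summary is by visit and regimen.

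Sampling time is described in several places:

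- Flowchart footnote d, for all regimens and with no tolerance: "Sampling for FVIII activity and antibodies should be scheduled to allow for a wash out of approximately 3 days".
- Section 9.8: "Assessments at visits must be performed prior to any trial product administration unless otherwise specified".
- Section 9.8.7.1: "Blood samples for FVIII activity will be collected pre-dosing (trough level"), with a footnote: "The trough level is defined as the lowest level of FVIII measure immediately prior to doing" (sic).
- Section 9, on visit timing: "Next visit in line must be calculated based on screening/V1". Nothing says which of a patient's weekly dosing gaps a visit should follow.

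Four exclusion rules are introduced as covering both pre-dose and post-dose activity. They concern the first doses after a regimen switch, a post-dose value not above the pre-dose value, a post-dose sample later than 90 minutes, and samples defrosted in transit. None concerns the interval before the pre-dose sample. The 90-minute rule excludes FVIII activity data generally, not just the post-dose value. A sensitivity analysis brings back everything except results around the first four doses after a switch.

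**The concern.** A pre-dose level means little without the hours since the previous dose, because FVIII falls by more than half each day at the stated half-life. Section 5.4 makes the clinical benefit of higher trough levels part of the trial's purpose, so readers will want to know whether an estimate is a 3-day level, the lowest level of the dosing week, or a mixture.

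The sampling text does not settle this. If footnote d fixes the time at about 3 days, a once-weekly patient is sampled well before the end of his interval, and the value is not his weekly trough. If footnote d sets only a minimum, a 7-day sample is allowed for once weekly, but a twice-weekly patient can then be sampled after either of two unequal gaps. Each reading leaves one regimen unclear, and the analysis neither models nor displays the actual times.

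The 90-minute rule is a separate matter of wording. A late post-dose draw cannot have affected a sample taken before that dose, yet the literal rule discards both.

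**Working it through.** The documents give no figure for a pre-dose level or its spread, so there is none to reproduce.

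**Inputs from the protocol.** Half-life 18.4 h (section 3.2.3, adult single-dose trial). Doses of 75 IU/kg once weekly and 50 IU/kg twice weekly from 12 years (Table 5-1).

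**Assumptions.** One-compartment decay at steady state; recovery R = 2 IU/dL per IU/kg (range 1.5 to 2.5); twice-weekly gaps of 72 and 96 h; endogenous floor F of 0, or 0.5 to 0.99 IU/dL (inclusion requires activity below 1%).

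**Once weekly, 3 days against 7 days.**
- Without a floor: 2^((168 − 72)/18.4) = 2^(96/18.4) = 37.2.
- Levels at R = 2, initial rise 75 × 2 = 150 IU/dL: 150 × 2^(−72/18.4) / (1 − 2^(−168/18.4)) = 9.98 at 72 h; the same with 168 h in the numerator gives 0.27.
- F = 0.5: (9.98 + 0.5)/(0.27 + 0.5) = 13.6. F = 0.99: (9.98 + 0.99)/(0.27 + 0.99) = 8.7.
- A value of 0.27 may lie below the LLOQ, which is not stated, and would then be set to half the LLOQ. At assumed LLOQs of 0.5, 1 and 2 IU/dL the no-floor ratio becomes 9.98/0.25 = 39.9, 9.98/0.5 = 20.0 and 9.98/1 = 10.0.

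**Twice weekly, 72 h against 96 h.** Let a = 2^(−72/18.4) = 0.0664 and b = 2^(−96/18.4) = 0.0269.
- Level before the dose that ends the 72 h gap: a(1 + b)/(1 − ab) = 0.0683 of the per-dose rise. After the 96 h gap: b(1 + a)/(1 − ab) = 0.0287.
- Ratio: 0.0683/0.0287 = 2.38. Other assumed half-lives: 2.02 at 22 h, 2.96 at 15 h.
- With a floor: (50R × 0.0683 + F)/(50R × 0.0287 + F). This runs from 1.94 (R = 1.5, F = 0.99) to 2.21 (R = 2.5, F = 0.5).
- Pooled geometric mean relative to the 72 h level, no floor, (1/2.38)^p for a share p of samples at 96 h: 0.92 at 10%, 0.81 at 25%, 0.65 at 50%.
- With equal 84 h gaps, or all samples at 3 days, there is no mixing of these two levels.

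**The 90-minute rule.** Its frequency is unknown, so assume 10% of pre-dose values are lost at random, with five samples per patient (the number of assessment visits named in section 9), residual SD 0.4 and between-patient SD τ on the log scale. The CI widens by sqrt[(τ² + 0.4²/4.5)/(τ² + 0.4²/5)]: 5.4% at τ = 0, 1.4% at τ = 0.3, 0.6% at τ = 0.5.

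**The case against.** The strongest reply is that footnote d does attach a nominal time to FVIII sampling. If sites kept to about 3 days, twice-weekly samples would cluster near 72 h and the estimate would be close to a 72 h level; 10% of samples at 96 h would move it only to 0.92 of that. This stands, and it rules out saying that the sampling has no intended time. What remains is that no tolerance is given, nothing planned shows adherence, and the same footnote sits badly with the trough definition for once weekly.

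A reader might infer that 3 days is only a minimum, from section 9.8.8.1: "A wash-out of approximately 3 days is required prior to blood sampling" and "A longer wash out period can be applied if the approximately 3 days wash out is not sufficient to avoid drug interference". But the first sentence concerns extra inhibitor tests at unscheduled visits, and the second concerns drug interference in confirmatory inhibitor samples. Neither governs scheduled FVIII sampling.

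A reader might also infer that the twice-weekly estimate is wrong by 2.4-fold, or that regimens will be misleadingly compared. The documents support neither. The 72/96 h split is assumed, 2.38 needs zero endogenous FVIII, and it is a possible spread, not a predicted bias. No FVIII test between regimens is planned, and because the investigator chooses the regimen, a side-by-side reading would stay confounded in any case.

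The protocol also allows further FVIII exclusions before database lock (section 10.2) and exploratory pharmacokinetic modelling (section 10.4). Both are discretionary and set no timing rule. On the 90-minute rule, the intent may well have been post-dose data only, and the sensitivity analysis restores the lost values, though together with defrosted samples.

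**Conclusion.** The point holds as a minor one. The plan neither models, limits nor displays time since last dose for pre-dose FVIII, and its sampling passages do not agree on what is measured under once weekly dosing. That conflict is the clearer and larger part: about 37-fold between a 3-day and a 7-day level without endogenous FVIII, and roughly 9 to 14-fold with an assumed floor of 0.5 to 0.99 IU/dL and recovery of 2 IU/dL per IU/kg. For twice weekly, mixing of levels about 1.9 to 2.4-fold apart is possible at the stated half-life. It depends on unequal gaps and on departures from 3 days, and may be slight or absent. All ratios rest on an adult single-dose half-life and mono-exponential decay.

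The consequence is an estimate that is harder to interpret, on a supportive endpoint. The primary safety endpoint is unaffected. The 90-minute wording costs about 0.6 to 5% in CI width if 10% of values were lost. A reader might infer bias from it, but nothing in the documents links a late post-dose draw to the trough.

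**What to change.** Reconcile flowchart footnote d with section 9.8.7.1 and its trough footnote, so that the intended FVIII sampling time is clear for each regimen. Which time applies is for the sponsor to state. Keep the planned model as the main analysis and add to Protocol 10.3.2.1 and SAP 2.3.2.1:

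1. *Each regimen's pre-dose estimate will be reported with the observed median and range of actual time since last dose. Observed pre-dose FVIII will be tabulated by regimen and time since last dose in non-overlapping bands: <60, 60 to <78, 78 to <90, 90 to <108, and ≥108 h.*
2. *As a sensitivity analysis, where times vary within a regimen, actual time since last dose will be added as a linear covariate, and the estimate reported at a stated time within the observed range.*
3. *The 90-minute exclusion applies only to post-dose activity and incremental recovery.*

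The cost is one table, one sensitivity model and a few lines of text. Dose times should already be derivable, because the ABR analysis is sub-grouped by time since last dose and the 90-minute rule needs both dose and sample times. The covariate's slope may be imprecise, and it cannot be estimated if all samples in a regimen follow the same gap; items 1 and 3 would still apply.
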